Management of Subjects with Missed Doses of Study Drug due to COVID-19
Pandemic**

If a subject misses a dose of study drug due to the COVID-19 pandemic, study drug administration may be continued. The following dosing schedules apply. For subjects with a missed dose(s) during the initial treatment period (Baseline to Week 16), study drug administration can be continued based on one of the following scenarios (see also **Diagram 1**, below):

1) Subject has missed one or more doses between Baseline and Week 16 but can come to the clinical site at Week 16 (see also **Diagram 2a**):

- Subjects who are clinical responders (IGA of 0/1 or EASI-75) at Week 16 can continue into the maintenance period.
- Subjects who are non-responders at Week 16 may be eligible to enroll in the long-term extension (LTE) study RD.06.SPR.118163.
- Subjects who required rescue therapy before Week 16 may be considered for the LTE study but will be required to continue with study visits until Week 16 visit is due.

2) Subject has no missed doses through Week 12 but cannot reach the clinical site at Week 16 (see also **Diagram 2b**):

- The Week 16 visit can be delayed by up to 8 weeks from the originally planned date. A remote Unscheduled visit should be planned between Week 12 and the delayed Week 16 visit for safety follow-up.
 - o Subjects who are clinical responders (IGA of 0/1 or EASI-75) at the rescheduled Week 16 visit can continue into the maintenance period.
 - o Subjects who are non-responders at the rescheduled Week 16 visit may be eligible to enroll in the LTE study.
- If the subject still cannot come to the delayed Week 16 visit within 8 weeks of the originally planned date, the delayed Week 16 visit should be performed remotely at the rescheduled date. A remote Unscheduled visit

CONFIDENTIAL

should be planned between Week 12 and the delayed Week 16 visit for safety follow-up. The subject may be considered for rollover into the LTE study after the delayed Week 16 visit is complete.

3) Subject has missed one or more doses between Baseline and Week 16 and cannot reach the clinical site at Week 16:

- For subjects who cannot come to the clinical site at week 12 but with an administered dose at Week 8 (with or without Week 4), the Week 12 visit can be delayed up to 3 weeks, and the Week 16 visit can be delayed up to 4 weeks from the rescheduled Week 12 visit (see also **Diagram 2c**).

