- For subjects with an administered dose at week 12 but with a missed dose at Week 4 and/or Week 8, the Week 16 visit can be delayed by up to 4 weeks from the originally planned date (see also Diagram 2d).
 - o Subjects who are clinical responders (IGA of 0/1 or EASI-75) at the rescheduled Week 16 visit can continue into the maintenance period.
 - o Subjects who are non-responders at the rescheduled Week 16 visit may be eligible to enroll in LTE study.
- For subjects with a missed dose at week 12, the Week 16 visit will be performed remotely at Week 16 (cannot be delayed) and the subject may be considered for rollover into the LTE study (see also **Diagram 2d**).

For subjects with a missed dose(s) during the maintenance treatment period (Week 16 to Week 48), study drug administration can be continued. Any visits where the subject cannot reach the site should be done remotely. If a subject misses three doses, the investigator must contact the Sponsor for further guidance.

- Subjects may be eligible to enroll in the LTE study at Week 48.
- Subjects who required rescue therapy may be considered for the LTE study but will be required to continue with study visits until the Week 32 visit is due.

CONFIDENTIAL

In all scenarios, study drug can be administered provided that there is a minimum 3 week interval between injections. If a subject cannot come to a planned visit due to COVID-19, the visit should be conducted remotely according to **Additional Measures for Subjects Amidst COVID-19 Pandemic**. Enrolment of subjects into the LTE study must be done in accordance with the LTE study protocol. Subjects who decline or are not eligible to enter into the LTE study will complete a follow-up visit 12 weeks after the last study drug injection.

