8.2. Key Definitions

Screening Period is a Period of approximately 2-4 weeks before Day 1/Baseline during which subject eligibility is evaluated and standardized background topical therapy is introduced over a run-in Period of at least 2 weeks before Day 1/Baseline.

The Initial Period is defined as Day 1/Baseline to Week 16 (before the Week 16 dose, with last dose at Week 12). If early discontinued during treatment period, it is defined as the period until 4 weeks after last dosing date or early termination date whichever is earlier.

The Maintenance Period is defined as Week 16 (Maintenance Baseline) to Week 48. If early discontinued during treatment period, it is defined as the period until 4 weeks after last dosing date or early termination date whichever is earlier.

Follow-up Period is defined as the post end of treatment period (i.e., 1 day after end of treatment period) to Follow-up visit in respective treatment period.

The Baseline value of the Initial Period will be taken as latest valid value prior to first injection of study drug. For subjects randomized but not treated, the Baseline value will be the latest value prior to the randomization. Week 16 measurements will serve as Baseline measurements for the Maintenance Period (i.e., Maintenance Baseline). If Week 16 measurements are missing for re-randomized subjects, the last valid non-missing measurement in the Initial Period (i.e., before the dosing for Maintenance Period at Week 16 visit) will be taken as the Baseline measurement for the Maintenance Period.

For diary data (e.g., Peak Pruritus (PP) NRS, Sleep disturbance (SD) NRS), the Baseline values will be the weekly prorated average of non-missing subject diary scores reported during the 7 days. A minimum of 4 daily scores out of the 7 days is required to calculate the weekly prorated average score. Refer the details for the analysis visit window for diary data in Section 8.4.

The date of first treatment is defined as the date of first injection of study drug. The date of first treatment is the Baseline date.

The date of last treatment is defined as the date of last injection of study drug.

Study day is defined as the number of days from the date of first treatment and will be calculated as follows:

This document is confidential.

- If the event date \geq date of first treatment, study day = event date – date of first treatment + 1. Study Day 1 is therefore defined as the day of first treatment.

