8.4. Analysis Visit Windows

Efficacy by-visit summaries will use the analysis visit. Unscheduled and early termination visits will be windowed based on the following analysis visit window which is based on study day. If multiple measurements are taken within the same window, the one taken closest to the target study day will be used for the analysis. If there are multiple measurements with same difference from target day, the later assessment should be used for the analysis.

Table 8-1: Analysis Visit Window

Analysis Visit	Target Study Day	Visit Window for EASI, IGA, BSA, SCORAD, Rescue therapy	Visit Window for PGIS-P, PGIS-SD, PGIC-P, PGIC-SD	Visit Window for DLQI/cDLQI, HADS, EQ-5D, POEM, WPAI:AD, Pain intensity/frequency, PGAD, PGAT, PIQs*
Baseline	1	<=1	<=1	<=1
Week 4	29	2 to 42	NA	NA
Week 8	57	43 to 70	2 to 81	2 to 84
Week 12	85	71 to 98	NA	NA
Week 15	106	NA	82 to 108	NA
Week 16	113	99 to 126	>=109	85 to 168 except for PIQs; >=85 for PIQs
Week 20	141	127 to 154	NA	NA
Week 24	169	155 to 182	NA	NA
Week 28	197	183 to 210	NA	NA
Week 32	225	211 to 238	NA	169 to 280 except for PIQs
Week 36	253	239 to 266	NA	NA
Week 40	281	267 to 294	NA	NA
Week 44	309	295 to 322	NA	NA

This document is confidential.

Statistical Analysis Plan for Interventional Studies

Sponsor: Galderma Research & Development, LLC; Protocol No.: RD.06.SPR.118161

Week 48	337	>=323	NA	>=281 except for PIQs
---------	-----	-------	----	-----------------------

* PIQs assessment is available during Initial period only. Visit window after Week 16 will not be applicable for PIQs.

Analysis visit of diary (ePRO) data will be defined depending on the data collection as below.

For the diary data at post-baseline visit, only the diary data assessed within the timeframe below (+1 hour to end time in spec) will be considered for analysis. If >1 diary recorded on a day (within window), only one of them to take for analysis (i.e. latest one for evening diary, earliest one for morning diary).

- Evening assessment (PP/AP NRS, Topical medication, PCS) recorded from 17:00:00 to 00:59:59
- Morning assessment (SD NRS, morning sleep diary) recorded from 5:00:00 to 17:59:59

Consecutive daily assessment:

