10.1. Primary Efficacy Endpoints and Analysis

10.1.1. Primary Analysis of Primary Efficacy Endpoint

Primary efficacy endpoint consists of the two co-primary endpoints:

- Proportion of subjects with an IGA* success (defined as an IGA of 0 [clear] or 1 [almost clear] and a ≥ 2 -point reduction from Baseline) at Week 16
- Proportion of subjects with EASI-75* ($\geq 75\%$ improvement in EASI from Baseline) at Week 16

* Further details regarding IGA and EASI-75 can be found in Sections 10.3.1 and 10.3.2 respectively.

Assessment results after taking rescue medication will be considered as treatment failure i.e. non-responders. Missing values at Week 16 will be treated as non-responder.

Both co-primary endpoints will be analyzed using a Cochran-Mantel-Haenszel test adjusted for the randomized stratification variables (IGA severity [3=moderate, 4=severe] and PP NRS [≥ 7 , < 7] for full population; IGA severity only for Baseline PP NRS ≥ 7 population) at 2.5% significance level (2-sided). In addition an unadjusted CMH test will be performed.

The proportion of subjects with IGA success and with EASI-75 at Week 16 will be summarized. The estimate of treatment unadjusted difference with the corresponding 2-sided 95% CI and strata-adjusted difference with the corresponding 2-sided 97.5% confidence interval, and p-values will be presented.

Bar charts for the proportions of subjects with IGA success and subjects with EASI-75 at Week 16 will be presented.

This document is confidential.

In addition, the proportion of subjects with IGA success will be analyzed using non-responder imputation on the ITT population excluding subjects who used the different version of IGA.

Additional summary tables for primary endpoints will also be presented by visit but excluding subjects from the visit summarized if the visit was affected by pandemic.

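### A COVID-delayed Week 16 visit can fall outside the SAP's Week 16 window for IGA and EASI, so a subject who enters maintenance as a responder can count as a co-primary non-responder

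*Protocol*

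**What the plan says.** **Protocol, Appendix 2 (missed doses due to COVID-19).** For a subject with no missed dose through Week 12 who cannot reach the site at Week 16 (scenario 2): "The Week 16 visit can be delayed by up to 8 weeks from the originally planned date". Then: "Subjects who are clinical responders (IGA of 0/1 or EASI-75) at the rescheduled Week 16 visit can continue into the maintenance period". Scenario 3 has two shorter allowances. If the Week 12 visit itself slips by up to 3 weeks, "the Week 16 visit can be delayed up to 4 weeks from the rescheduled Week 12 visit". If the Week 12 dose was given but an earlier one was missed, "the Week 16 visit can be delayed by up to 4 weeks from the originally planned date".

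**SAP 8.2.** "Study Day 1 is therefore defined as the day of first treatment". The Initial Period ends before the Week 16 dose. If a re-randomised subject has no Week 16 value, the last valid pre-dose value from the Initial Period serves as Maintenance Baseline.

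**SAP 8.4.** "Efficacy by-visit summaries will use the analysis visit". Also: "Unscheduled and early termination visits will be windowed based on the following analysis visit window which is based on study day". Table 8-1 gives Week 16 IGA and EASI a target of Day 113 and a window of Days 99 to 126. Days 127 to 154 are Week 20 and Days 155 to 182 are Week 24. For DLQI and similar questionnaires, Week 16 runs from Day 85 to Day 168. The end of 8.4 applies the closest-to-target rule to scheduled and unscheduled efficacy assessments alike and exempts only safety and pharmacokinetic data from windowing.

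**SAP 10.1.1.** "Missing values at Week 16 will be treated as non-responder". Protocol 10.1.3 has the same rule.

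**The concern.** The two documents can give one assessment two meanings. The protocol treats the rescheduled visit as Week 16 and uses it to declare response. The SAP windows can label the same assessment as a maintenance visit, leave Week 16 empty and score the subject as a failure.

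Baseline IGA must be at least 3, so an IGA of 0 or 1 always carries the required 2-point reduction. Every subject who enters maintenance as a responder therefore meets at least one co-primary endpoint at that visit, and scoring the subject as a failure on both contradicts the observed data.

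The label also conflicts with the rest of the SAP. Under 8.2 a value taken before the Week 16 dose is Initial Period data and can be the Maintenance Baseline, so it should not carry a maintenance label. At a visit on Day 150, DLQI would be Week 16 while IGA and EASI would be Week 20.

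**Working it through.** **1. Reproduce the SAP window.** With first treatment as Day 1, the target for week w is 7w + 1. Weeks 12, 16 and 20 fall on Days 85, 113 and 141. The midpoints are (85 + 113)/2 = 99 and (113 + 141)/2 = 127, so Week 16 covers Days 99 to 126, as in Table 8-1.

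**2. Map the permitted delays.**

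| Case | Visit 6 study day | Table 8-1 label for IGA/EASI |
|---|---|---|
| Delay of 0 to 13 days | 113 to 126 | Week 16 |
| Delay of 14 to 41 days | 127 to 154 | Week 20 |
| Delay of 42 to 56 days | 155 to 169 | Week 24 |
| Scenario 2 maximum | 113 + 56 = 169 | Week 24 |
| Scenario 3, Week 12 visit slipped, maximum | 85 + 21 + 28 = 134 | Week 20 |
| Scenario 3, earlier dose missed, maximum | 113 + 28 = 141 | Week 20 |

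**3. Could another value fill the Week 16 window?** In scenario 2 the interim contact is a remote safety visit, and the remote assessment list in Appendix 2 contains neither IGA nor EASI. Week 16 stays empty. The same holds in scenario 3 when the Week 12 visit was on time. When the Week 12 visit slipped by 14 to 21 days it falls on Days 99 to 106, inside the Week 16 window. Week 16 is then not missing but filled by the Week 12 assessment, while the real Visit 6 (Days 127 to 134, four weeks later) becomes Week 20.

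**4. Size.** The documents give no count. Assume that 1% to 3% of subjects are delayed beyond 13 days, and take the protocol's maintenance planning rates of 45% and 12% responding. Nemolizumab: 500 × 0.01 × 0.45 = 2.25 to 500 × 0.03 × 0.45 = 6.75, or about 2 to 7 subjects. Placebo: 250 × 0.01 × 0.12 = 0.3 to 250 × 0.03 × 0.12 = 0.9.

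If a share f of responders is reclassified in both arms, each difference is multiplied by (1 − f). Power is Φ[(Δ − z·SE0)/SE1], with SE0 from the pooled rate, SE1 from the separate rates and z for two-sided 2.5%. The design rates are 30% v 12% (IGA) and 49% v 19% (EASI-75). At f = 0 with 500 v 250 subjects, power is 99.99% for IGA and higher for EASI-75, which reproduces the stated figure of more than 99%. The last column takes a PP NRS ≥ 7 population at its 250-subject minimum, allocated 2:1.

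| f | IGA difference (points) | EASI-75 difference (points) | IGA power, N = 750 | IGA power, N = 250 |
|---|---|---|---|---|
| 0 | 18.0 | 30.0 | 99.99% | 84.8% |
| 1% | 17.8 | 29.7 | 99.98% | 84.2% |
| 3% | 17.5 | 29.1 | 99.98% | 83.0% |
| 5% | 17.1 | 28.5 | 99.97% | 81.8% |
| 10% | 16.2 | 27.0 | 99.94% | 78.6% |
| 20% | 14.4 | 24.0 | 99.77% | 71.0% |

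**5. Time since last dose.** In scenario 2 the last dose is at Week 12: 169 − 85 = 84 days, or 12 weeks.

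**6. Maintenance labels.** Week 48 is targeted at Day 337. That is 337 − 113 = 224 days (32 weeks) after an on-time re-randomisation, but 337 − 169 = 168 days (24 weeks) after the latest one. Across delays of 14 to 56 days, clinic assessments can reflect 2 to 8 fewer weeks of maintenance than their label suggests.

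**The case against.** **The label is not forced.** The SAP sentence that applies Table 8-1 names only unscheduled and early termination visits. Protocol 8.5.2 says that a visit outside its window is not an unscheduled visit, and Appendix 2 still calls this one the Week 16 visit. One can argue that it keeps its nominal label. This has some weight, so misclassification cannot be stated as certain. Against it stand the use of the analysis visit for efficacy, the rule covering scheduled and unscheduled assessments, and the exemption for safety and pharmacokinetics only. The nominal reading brings its own mismatch: the composite key secondary endpoints would pair IGA or EASI from as late as Day 169 with PP NRS from Days 106 to 112, extendable by 5 days at either end.

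**Text is blacked out.** SAP 10.1.1 refers to 10.3.1 and 10.3.2 for IGA and EASI details, and those sections and the Appendix 2 diagrams cannot be read. A mapping rule may be there. The point concerns the visible text, in which none appears.

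**Other analyses cover it.** Tipping-point analysis would treat these subjects as missing and so bound the effect. Multiple imputation would replace, and LOCF would overwrite with an earlier value, a result that was actually observed. The pandemic tables drop affected visits. None uses the rescheduled value as Week 16.

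**A Day 169 value is a poor Week 16 value.** It comes 12 weeks after the last dose, which the protocol equates to about 5 half-lives. This stands, and it is why both versions should be shown.

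**Some discordance is intended.** Entry to maintenance needs IGA 0/1 or EASI-75, so failing one co-primary endpoint is possible by design. Failing both is not.

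**Conclusion.** The protocol and SAP conflict for any Visit 6 delayed by 14 days or more. On the more natural reading, the co-primary result contradicts the responder status used for maintenance. The derivation of a co-primary endpoint should be settled before unblinding.

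The size rests on assumptions. At 1% to 3% of subjects delayed, about 2 to 7 nemolizumab responders are affected and the IGA difference loses about 0.2 to 0.5 points. Full-population power stays above 99% even if 20% of responders are reclassified. The PP NRS ≥ 7 population at its minimum size is more sensitive, but at 1% to 3% IGA power falls by less than 2 points.

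A reader might infer more than the documents support:

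- That the primary result is at risk or biased towards the drug. With equal shares lost in both arms the error shrinks the difference.
- That every maintenance window is tied to Day 1. Maintenance PP, AP and SD NRS at attended visits run back from the actual visit date, and protocol 8.4.7 itself schedules visits from Day 1. Maintenance endpoints are only summarised descriptively, so no test is affected.
- That the late value must be the sole primary value. Keeping the strict window as primary is defensible if the SAP says so and reports the other version.

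**What to change.** Before unblinding:

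1. **SAP 8.4.** State that the last IGA and EASI at the rescheduled Visit 6, before the Week 16 dose or re-randomisation, are assigned to Week 16 and never labelled as a maintenance visit. State that this overrides the closest-to-target rule, so that a slipped Week 12 visit does not take the Week 16 place.
2. **Paired sensitivity analysis of the co-primary endpoints.** Accept Visit 6 values only on Days 99 to 126 and count later ones as non-response. If the sponsor prefers the strict window as primary, run the mapped version as the sensitivity analysis.
3. **Composite key secondary endpoints.** For delayed subjects, repeat them with PP NRS from the week before the rescheduled visit, as a sensitivity analysis only. Each subject then keeps one primary Week 16 PP NRS value.
4. **Maintenance.** Add a descriptive summary by time since re-randomisation for delayed subjects.
5. **Reconcile** Appendix 2 with SAP 8.2 and 8.4 in the text, leaving every dosing and visit rule as it is.

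The cost is SAP wording, one derived date and a few extra tables. The drawback is that a few primary Week 16 values would be later than nominal, which item 2 exposes.

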11.2 Monitoring

On-site interim monitoring visits may not be feasible during COVID-19 restrictions; therefore, remote monitoring will be completed until on-site monitoring can be conducted again. Site monitoring activity will comply with the processes documented within the COVID-19 Site Management Risk Assessment Form.

CONFIDENTIAL

Diagram 1. Flow Chart of Management of Subjects with Missed Visits Before Week 16 due to COVID-19

[figure not shown]
[figure not shown]
[figure not shown]

Diagram 2. Management of Subjects Based on Missed Dosing Scenarios

[figure not shown]
a. Diagram of Management of Subjects due to Scenario 1

b. Diagram of Management of Subjects due to Scenario 2

[figure not shown]

c. Diagram of Management of Subjects due to Scenario 3: Cannot reach site at Visit 12

d. Diagram of Management of Subjects due to Scenario 3: Cannot reach site at Visit 16

③ One or more missed visits between BL and W16 and subject cannot reach the clinical site at W16

6 / CONFIDENTIAL

CONFIDENTIAL

Appendix 3: CYP Substrates with Narrow Therapeutic Index

CYP enzymes	Substrates with narrow therapeutic index ⁽¹⁾
CYP1A2	Theophylline, Tizanidine
CYP 2B6	-
CYP2C8	Paclitaxel
CYP2C9	Warfarin, Phenytoin
CYP2C19	S-mephenytoin
CYP3A	Alfentanil, Astemizole, Cisapride, Cyclosporine, Dihydroergotamine, Ergotamine, Fentanyl, Pimozide, Quinidine, Sirolimus, Tacrolimus, Terfenadine
CYP2D6	Thioridazine, Pimozide

(1) CYP substrates with a narrow therapeutic index refers to drugs whose exposure-response relationship indicates that small increases in their exposure levels by the concomitant use of CYP inhibitors may lead to serious safety concerns (eg, Torsades de Pointes). This is not an exhaustive list.

Source: Center for Drug Evaluation and Research (CDER), Food and Drug Administration, U.S. Department of Health and Human Services. Guidance for Industry: Drug Interaction Studies—Study Design, Data Analysis, Implications for Dosing, and Labeling Recommendations (Draft Guidance). February 2012.

CONFIDENTIAL

Appendix 4: Investigator's Global Assessment (IGA)

Status	Score	Definition
Clear	0	Minor, residual hypopigmentation/hyperpigmentation, no erythema or induration/papulation, no oozing/crusting.
Almost clear	1	Trace faint pink erythema, with barely perceptible induration/papulation and no oozing/crusting.
Mild	2	Faint pink erythema with mild induration/papulation and no oozing/crusting.
Moderate	3	Pink-red erythema with moderate induration/papulation with or without oozing/crusting.
Severe	4	Deep or bright red erythema with severe induration/papulation with oozing/crusting.

Source: Paller AS, Tom WL, Lebwohl MG, et al. Efficacy and safety of crisaborole ointment, a novel, nonsteroidal phosphodiesterase 4 (PDE4) inhibitor for the topical treatment of atopic dermatitis (AD) in children and adults. *J Am Acad Dermatol.* 2016;75(3):494-503.e6.

CONFIDENTIAL

Appendix 5: Eczema Area and Severity Index (EASI)

Body region	EASI score
Head/Neck (H)	$(E + I + Ex + L) \times Area \times 0.1$
Upper limbs (UL)	$(E + I + Ex + L) \times Area \times 0.2$
Trunk (T)	$(E + I + Ex + L) \times Area \times 0.3$
Lower limbs (LL)	$(E + I + Ex + L) \times Area \times 0.4$
EASI =	Sum of the above 4 body region scores

The degree of severity of each sign (E=erythema, I=induration/papulation, Ex=excoriation, L=lichenification) in each of the 4 body regions is evaluated based on a scale ranging from 0 to 3 (0: none; 1: mild; 2: moderate; 3: severe), with half points allowed.

Area (the affected body area) is defined as follows: 0=0%; 1=1-9%; 2=10-29%; 3=30-49%; 4=50-69%; 5=70-89%; 6=90-100%. Among the four zones, trunk includes the genital area, and lower limbs include the buttocks.

Source: Hanifin JM, Thurston M, Omoto M, Cherill R, Tofte SJ, Graeber M. The Eczema Area and Severity Index (EASI): assessment of reliability in atopic dermatitis. EASI Evaluator Group. Exp Dermatol. 2001;10(1):11-8.

CONFIDENTIAL

